1.4 Benefit/risk and ethical assessment

1.4.1 Individual benefit

There is no individual benefit to the patients included in the study.

1.4.2 Collective benefit

It is therefore important to identify specific molecular targets that can be used for targeted cancer therapy, thereby limiting the progression and metastasis of this invasive tumor and improving patient outcomes.

Although a challenge, the development of a targeted therapy for the treatment of TNBC is greatly needed and as it is essential that these patients gain access improved treatment regimens.

CAIX, a cell surface antigen expressed in TNBC with a low expression level in normal tissues seems, thereby highlighting its potential value as a therapeutic target. girentuximab is a monoclonal antibody that recognizes CAIX. The extensive clinical experience with radiolabeled girentuximab has provided strong clinical evidence to support its use as a targeted PET imaging agent.

The initial objective of this study is to evaluate the biodistribution of ⁸⁹Zr-girentuximab using PET-CT (immuno-PET) imaging, which will allow us to show that CAIX could be a promising target and that the immuno-PET imaging tracer could act as an effective companion imaging diagnostic when screening patients for future therapies.

A secondary objective, is to provide preliminary clinical data that after screening patients with CAIX immuno-PET, the girentuximab has the potential to be radiolabeled with a therapeutic radionuclide such as Lutetium-177 (¹⁷⁷Lu) to treat TNBC metastases in future clinical trials.

1.4.3 Overall risks

In previous clinical studies, administration of Zirconium-89 (⁸⁹Zr) labeled monoclonal antibodies was proven to be safe.

Although never observed in previous trials, allergic-type reactions are possible during and immediately following the administration of girentuximab. In a total of more than 2000 administrations of radiolabeled murine and chimeric girentuximab to humans, no allergic-type reaction was observed.

In clinical studies administration of (⁸⁹Zr) labelled monoclonal antibodies were proven to be safe (40,43).

Patients will be carefully monitored after ⁸⁹Zr-Girentuximab administration.

1.4.4 Benefit / risk balance

There is more than 20 years of experience in humans with SPECT/CT imaging using girentuximab labelled with various radioligands including ¹²⁴I and ¹¹¹In. These studies investigated the pharmacokinetics, toxicity, immunogenicity, and imaging characteristics of radiolabelled girentuximab in kidney cancer patients.

In a clinical phase 1 study investigating safety, tolerability, imaging characteristics, biodistribution and dosimetry, ⁸⁹Zr-TLX250 was found to be safe, and to provide improved imaging characteristics, compared to ¹²⁴I-girentuximab, in line with preclinical findings (44). The clinical development of ⁸⁹Zr-Girentuximab has found the optimal dose of radioactivity to 37 MBq ± 10% of ⁸⁹Zr with a total dose of girentuximab of 10 mg.

Preliminary safety data in the ZIRDOSE study using ⁸⁹Zr-girentuximab, administered ⁸⁹Zr-TLX250 to 5 patients at 5 mg and 10 mg girentuximab mass dose, each, did not prompt any safety concern. In the course of the study, no treatment-related SAEs or SUSARs were reported from any of the 10 patients. A total of 7 AEs were experienced in 4 patients. An unlikely AE or no relationship to treatment was assessed by the investigator for 6 AEs. Mild nausea in one patient was considered by the investigator as possibly related to the study treatment.

In previous ⁸⁹Zr-TLX250 clinical studies, all patients had a whole body PET/CT scan. The CT scans were a low-dose CT for the purpose of attenuation correction of the PET data. Because acquisition parameters for the low-dose CT were restricted, the radiation dose from the low-dose CT was approx. 3 mSv.

Radiation dosimetry was evaluated in a bridging dosimetry study (ZIRDOSE study) investigating the safety and tolerability of ⁸⁹Zr-girentuximab. The whole body effective dose for administration of ⁸⁹Zr-girentuximab in this phase 1 study was 0.487 ± 0.014 mSv/MBq using the most widely

established dose calculation tool OLINDA 1.1 and the ICRP 60 standard (45). The absorbed/effective dose was calculated accordingly and resulted in a total whole body effective dose of 18.0 ± 0.5 mSv for 37 MBq. When a newer software IDAC-Dose 2.1 and the ICRP 103 standard (46) is used, the resulting effective dose will be 0.551 ± 0.030 mSv/MBq or 20.5 ± 1.1 mSv for 37 MBq.

The combined whole body effective dose of ^{89}Zr -girentuximab administration and low-dose CT is expected to be below 20 mSv based on the accepted standard OLINDA 1.1 and ICRP 60, or below 23 mSv based on IDAC-Dose 2.1 and ICRP 103, for all patients. The lifetime attributable risk for incidence of radiation-induced cancer for an effective dose of 23 mSv is 0.4% (ICRP 103, 2007), which is comparable to the risk from a diagnostic CT of chest, abdomen and pelvis (47).

Given the well-known safety and tolerability of radiolabelled girentuximab, confirmed for ^{89}Zr -TLX250 in the context of a phase I safety study, and further considering the low antibody doses used in this study, no harmful effects exceeding the risk of established diagnostic imaging procedures are to be expected. The results of this study may contribute to the development of a new targeted therapy for TNBC, it appears that the benefit/risk ratio will be clearly in favour of the benefit to the patient. Indeed, if the imaging can clinically substantiate a potential new imaging and therapeutic target, this imaging agent could become a "companion imaging diagnostic" used to screen patients that have a higher likelihood of responding to a CAIX-targeted therapeutic radiolabelled with ^{177}Lu . Although, highly unlikely, ^{89}Zr -TLX250 may cause allergic-type reactions. The study sites are well equipped to treat allergic/anaphylactic reactions.

2. OBJECTIVES

2.1 Primary objective(s) and endpoint

2.1.1 Primary objective

To assess the concordance for tumor lesion detection using ^{89}Zr -TLX250 PET/CT versus a conventional ^{18}FDG PET/CT scan where comparison will be made on a per lesion analysis basis.

2.1.2 Endpoints of primary objective

Concordance study of metastatic uptake seen in ^{18}FDG PET/CT scan and ^{89}Zr -TLX250 PET/CT scan per "lesion" by comparing for each lesion the CT scan, ^{18}FDG PET scan and ^{89}Zr -TLX250 PET/CT scan by assessing a ratio "Number of positive or negative ^{89}Zr -TLX250 lesions / Number of positive or negative FDG lesions" and "Number of positive or negative ^{89}Zr -TLX250 lesions / Number of CT scan lesions".

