5.2.3 Imaging Analysis

5.2.3.1 ⁸⁹Zr-TLX250 Tumor Targeting

⁸⁹Zr-TLX250 tumor uptake will qualitatively be assessed, considering whether or not ⁸⁹Zr-TLX250 binding the target lesions determined on FDG PET-CT as metastatic lesions.

The interpretation of the ⁸⁹Zr-TLX250 PET/CT images as positive or negative for metastatic TNBC will be made on the basis of visual examination only.

The ⁸⁹Zr-TLX250 PET/CT images will be evaluated for evidence of radioactive uptake in the metastatic TNBC lesions. The local and central reviewers will designate the lesions as having a status of positive or negative.

The ⁸⁹Zr-girentuximab PET/CTs will be assessed in a central reviewing system to ensure true lesion detection and reproducible inter-observer agreement. All ⁸⁹Zr-girentuximab PET/CTs would be assessed by two expert nuclear physicians independently.

The first evaluation will be done by the nuclear physician, in charge of the patient during the ⁸⁹Zr-girentuximab PET/CT exam.

The second evaluation will be done by a second nuclear physician who should be blinded for evaluation of the first nuclear physician. However, for patient safety reasons, the nuclear physician should be allowed to communicate findings that required (local) interventions (e.g. brain metastases).

The two reports would be harmonized to one final report by the first reviewer. In case of different findings, a third nuclear physician should evaluate the ⁸⁹Zr-girentuximab PET/CT exam to reach a consensus.

A tumor lesion will be defined visually positive based on anatomical substrate on low-dose CT in combination with ¹⁸FDG and/or ⁸⁹Zr-girentuximab-uptake. Quantification of positive lesions as defined by evaluation reports for ¹⁸FDG and ⁸⁹Zr-girentuximab PET/CT will be performed by drawing regions-of-interest using dosisoft (PLANET Edition 3 – PLANET Onco Dose, Version 3.1.1.50 – 2021-01-03).

The maximum and mean standardized uptake values (SUV) will be calculated. SUVmax will be used for tumor tracer-uptake; SUVmean for measuring uptake in healthy organs and blood pool.

The lesion will be classified as PET-positive if:

- Radioactivity in the lesion is clearly visible (as described above), **AND**
- With a same location as FDG positive lesions described previously.

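### The primary 89Zr/FDG lesion ratio does not measure per-lesion concordance, and section 5.2.3.1 gives two conflicting rules for a positive lesion

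*Combined protocol and SAP*

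**What the plan says.** The primary objective (2.1.1, repeated in 8.1.1) is concordance of lesion detection between 89Zr-TLX250 PET/CT and FDG PET/CT, and "comparison will be made on a per lesion analysis basis". The endpoint (2.1.2, repeated in 8.1.2) is to be assessed "by comparing for each lesion the CT scan" and the two PET scans, through two ratios. The first is "Number of positive or negative ^{89}Zr -TLX250 lesions / Number of positive or negative FDG lesions", so its denominator is the "Number of positive or negative FDG lesions". The second has the same numerator over the "Number of CT scan lesions".

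Section 5.2.3.1 makes the 89Zr reading binary: "The local and central reviewers will designate the lesions as having a status of positive or negative". It then gives two accounts of positivity. The first is "A tumor lesion will be defined visually positive based on anatomical substrate on low-dose CT in combination with" uptake of FDG, of 89Zr-girentuximab, or of both. The second closes the section and makes PET positivity conditional on clearly visible activity and on a further requirement: "With a same location as FDG positive lesions described previously".

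Two other places matter. Secondary endpoint 1 (2.2.2; numbered 4 in 8.1.4) is the number of 89Zr-positive lesions over the number of FDG-positive lesions. Section 8.8.2 sets the lesion total as every lesion found by at least one modality and plans kappa with a 95% CI for agreement between modalities, together with McNemar tests and detection rates. It places these under a preliminary analysis of diagnostic performance and does not name any of them as the primary analysis.

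**The concern.** Concordance concerns the same lesion seen on two scans. A ratio of two counts carries no information about pairing, so it can equal 1.0 when the scans agree on every lesion and when they agree on none. A primary result of 1.0 would invite the conclusion that the tracers are interchangeable. Sections 1.2 and 1.3 say that CAIX is expressed in only 25% of triple-negative tumours, so disagreement with FDG is to be expected and is what the study should describe.

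The conflict in 5.2.3.1 decides whether one kind of disagreement can exist at all. If 89Zr positivity requires an FDG-positive site, a lesion seen only on 89Zr is excluded by definition. Two analysts could each follow the document and report different primary results.

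**Working it through.** The plan gives no expected value for the ratio and no expected lesion counts, and 8.2 says that the 12 patients were not chosen on statistical grounds. There is no figure to reproduce. The check is algebra on a paired table, and every count below is an assumption.

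**Notation.** Over one lesion list: a = 89Zr+/FDG+, b = 89Zr-/FDG+, c = 89Zr+/FDG-, d = 89Zr-/FDG-, n = a+b+c+d. A shared list follows from the per-lesion comparison in 2.1.2 and the union total in 8.8.2. On that list, d lesions are those seen on CT only.

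**1. Literal reading of the first ratio.** (a+c+b+d)/(a+b+c+d) = n/n = 1 for any data, provided that every lesion is evaluable on both tracers. The second ratio is different: with 40 listed lesions and 40, 30 or 20 seen on CT, it is 1.0, 1.33 or 2.0.

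**2. Reading as like over like.** Positives: (a+c)/(a+b). Negatives: (b+d)/(c+d). Both use margins only. Set each tracer at 30 positives. Since c > 0 in the second and third rows, this is possible only if uptake on either tracer may define a lesion.

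| Overlap a | b = c | Positives ratio | a/(a+b) | c/(a+c) | Kappa, 60 sites | Kappa, d = 0 |
|---|---|---|---|---|---|---|
| 30 | 0 | 1.0 | 100% | 0% | 1.0 | undefined |
| 25 | 5 | 1.0 | 83% | 17% | 0.67 | -0.17 |
| 20 | 10 | 1.0 | 67% | 33% | 0.33 | -0.33 |

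For overlap 25 with 60 sites (d = 25): observed agreement = 50/60 = 0.833, expected = 0.5, kappa = 0.333/0.5 = 0.67. With d = 0: n = 35, observed = 25/35 = 0.714, expected = (30×30 + 5×5)/35² = 0.755, kappa = -0.041/0.245 = -0.17. Kappa therefore depends strongly on the assumed CT-only lesions; the ratio and a/(a+b) do not.

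At the extremes, (a,b,c,d) = (20,0,0,20), (10,10,10,10) and (0,20,20,0) give overall agreement (a+d)/n of 100, 50 and 0%, while the literal, positives and negatives ratios are all 1.0 each time.

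**3. Same-location rule.** Now c = 0 always. The positives ratio becomes a/(a+b), the share of FDG-positive lesions that are 89Zr-positive. This is matched by lesion but runs in one direction, and it is identical to secondary endpoint 1. It takes no account of FDG-negative lesions: (15,15,0,10) and (15,15,0,2) both give 0.50, while overall agreement is 25/40 = 62.5% and 17/32 = 53%, kappa is 0.33 and 0.11, and the negatives ratio is 25/10 = 2.5 and 17/2 = 8.5.

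**4. Effect on 8.8.2.** With c = 0, 89Zr can never detect a lesion that FDG misses. Every FDG/89Zr discordance entering kappa and the paired comparisons falls on the same side.

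**The case against.** The literal reading is probably not what the authors meant. The comparison is described lesion by lesion, secondary endpoint 1 writes out a positives-only ratio, and the natural intention is one ratio for positives and one for negatives. That is fair, but the second step above shows that this reading is still a comparison of margins.

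The study is also a descriptive pilot with no success threshold, interim look or sample-size calculation resting on the ratio. That limits the consequences, but a descriptive study still needs a primary endpoint with one meaning.

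A reader might infer three stronger things, and the documents do not support them:

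- *Both primary ratios are forced to 1.* Only the 89Zr/FDG ratio is, and only when read literally. The CT ratio has a different denominator.
- *The plan has no lesion-level agreement statistic.* Section 8.8.2 plans kappa with a confidence interval on a union lesion list, and McNemar tests. What is missing is the link to the primary endpoint. Kappa also inherits the unresolved positivity rule.
- *The formula fails in the same way under either positivity rule.* Under the same-location rule the positives ratio is a legitimate lesion-matched proportion. The margins criticism needs the either-tracer rule; the criticism that one direction is defined away needs the same-location rule. They are alternatives, and the plan does not say which applies.

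**Conclusion.** The point holds for the 89Zr/FDG ratio in 2.1.2 and 8.1.2. It is uninformative if read literally, blind to pairing if read as like over like under the either-tracer rule, and a one-directional duplicate of secondary endpoint 1 if read as positives over positives under the same-location rule. None of these is concordance in both directions. The contradiction in 5.2.3.1 is real whichever reading is taken.

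The size is illustrative: a ratio of 1.0 is compatible with 67 to 100% of FDG-positive lesions being 89Zr-positive in the 30/30 example, and with overall agreement anywhere from 0 to 100% at the extremes. This rests on assumed lesion counts, a list common to the scans and no unevaluable lesions. The kappa values rest in addition on the assumed number of lesions negative on both PET scans. No sample-size statement is affected. This is an endpoint that is wrong as written, not merely one lacking detail, and it should be settled before analysis.

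**What to change.** - **2.1.2 and 8.1.2:** replace the ratios with paired 2x2 lesion tables, 89Zr by FDG and 89Zr by CT, over the union list already defined in 8.8.2. Define primary concordance from these tables by reporting both directions: the share of FDG-positive lesions that are 89Zr-positive, a/(a+b), and the share of 89Zr-positive lesions that are FDG-negative, c/(a+c). Report overall agreement and the planned kappa beside them, and do the same against CT.
- **8.8.2:** state that this kappa and lesion list serve the primary endpoint.
- **5.2.3.1:** keep the same-location rule only for matching lesions across scans, and remove it as a condition of 89Zr positivity.
- **2.2.2 and 8.1.4:** say how secondary endpoint 1 differs from the primary measure, for example by keeping it as the count-based burden ratio.

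The cost is rewording in these sections. No new data or reads are needed, provided that the planned reads record 89Zr uptake away from FDG-positive sites, as the either-tracer sentence already implies.

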2.2.2 Endpoints of secondary objectives

1. Percent of positive CA IX metastatic tumor burden compared to total metastatic tumor burden by ^{18}FDG (ratio "Number of positive ^{89}Zr -TLX250 lesions / Number of positive FDG lesions")
2. If a metastasis biopsy is conducted, assessment of the correlation between the normalized uptake values (SUV) of ^{89}Zr -TLX250 positive lesions and CAIX histological expression will be done by comparing the ^{89}Zr -TLX250 semi-quantitative data with the immunohistochemical results (IHC) of biopsied metastases.
3. The safety and tolerability of ^{89}Zr -TLX250 will be evaluated by measuring and monitoring vital signs within 2 hours after injection of the radiopharmaceutical. The patient will be informed that in the event of abnormal physical signs, occurring within 24 hours after ^{89}Zr -TLX250 administration, he must report them to the investigator for

registration. The reporting period of AEs (related to ^{89}Zr -TLX250) and SAEs cover a period of 30 days after ^{89}Zr -TLX250 administration.

- ⇒ The NCI Common Toxicity Criteria, version 5.0 reference will be used.
- ⇒ HACA (Human anti-chimeric antibody) will be assessed.

2.3 Exploratory objective(s)

2.3.1 Exploratory objectives

For 3 to 5 patients, assessment of the absorbed doses received by organ and in whole body after ^{89}Zr -TLX250 administration for imaging purpose in metastatic TNBC patients.

2.3.2 Endpoints of Exploratory objectives

For 3 to 5 patients, quantitative biodistribution of ^{89}Zr -TLX250 will be evaluated from sequential **whole body PET-CT imaging and pharmacokinetic data** (blood samples) taken at **D0** (before and after ^{89}Zr -TLX250 administration), **D1, D3, D5** and **D7**.

3. STUDY DESIGN

3.1 Overview of study design

The research presents the following characteristics:

- feasibility study
- Imaging Study
- Pilot trial
- Monocentric
- Non randomized
- Uncontrolled
- Open-label
- Prospective

3.2 Study design schedule

[figure not shown]

Figure 1: Study design schedule

3.3 Study discontinuation

The study could be interrupted or terminated by the sponsor in agreement with the coordinator and with the competent authorities for the following reason:

- frequency and/or unexpected severity of the toxicity,
- recruitment of patients too low,
- poor quality of the data collected,

4. PATIENT SELECTION

Each patient should meet all of the inclusion criteria and none of the non-inclusion criteria for this study. Under no circumstances can there be exceptions to this rule.

If they meet the inclusion and non-inclusion criteria, patients will be offered the research after discussion with a nuclear physician in charge of the study. The latter will present the study as well as the benefits and risks of the trial procedure. The patient will be given the necessary reflection time before signing the consent form.

4.1 Population description

Patients with Triple Negative Breast Cancer recurrence.

4.2 Inclusion criteria

Patients must meet all of the following inclusion criteria to be eligible for enrolment into the study:

1. Written informed consent obtained from the patient prior to performing any protocol-related procedures, including screening evaluations.
2. Female or male, Age \geq 18 years at time of study entry.
3. Primitive triple negative breast cancer proven histologically, defined according to the following criteria:
 - ⇒ Estrogen receptors \leq 10%.
 - ⇒ And progesterone receptors \leq 10%.
 - ⇒ And HER2 not amplified or not overexpressed.
4. Metastatic Breast Cancer documented by conventional imaging and/or FDG PET/CT with at least one measurable metastatic lesion according to RECIST and/or PERCIST.
5. Consent to use a contraception method for at least 30 days after administration of ^{89}Zr -TLX250.
6. ECOG Performance Status 0 or 1.
7. Life expectancy at least 6 months.
8. Patient has valid health insurance.
9. Patient is willing and able to comply with the protocol for the duration of the study including undergoing treatment and scheduled visits and examinations including follow up.

4.3 Non-inclusion criteria

Patients should not enter the study if any of the following non-inclusion criteria are fulfilled:

1. History of another primary malignancy except for basal cell carcinoma within the last 5 years.
2. Chemotherapy, radiotherapy, or immunotherapy within 4 weeks prior to the planned administration of ^{89}Zr -TLX250 or continuing adverse effects ($>$ grade 1) from such therapy (Common Terminology Criteria for Adverse Events [CTCAE] version 5.0).

3. Planned antineoplastic therapies (for the period between IV administration of ^{89}Zr -TLX250 and imaging).
4. Exposure to murine or chimeric antibodies within the last 5 years.
5. Previous administration of any radionuclide within 10 half-lives of the same.
6. Impossibility to hold lying motionless at least 1 hour, or known claustrophobia.
7. Serious non-malignant disease (e.g. psychiatric, infectious, autoimmune or metabolic), that may interfere with the objectives of the study or with the safety or compliance of the subject, as judged by the investigator.
8. Mental impairment that may compromise the ability to give informed consent and comply with the requirements of the study.
9. Pregnant or likely to be pregnant or nursing patient.
10. Known hypersensitivity to girentuximab or desferoxamine.
11. Renal insufficiency with GFR $\leq 45 \text{ mL/min/1.73 m}^2$.
12. Persons deprived of their liberty, under a measure of safeguard of justice, under guardianship or placed under the authority of a guardian.
13. Disorder precluding understanding of trial information or informed consent.

Participation to another interventional therapeutic clinical trial is not authorized.

Procedures for withdrawal of incorrectly enrolled patients are presented in Section 4.4.

If a patient withdraws from participation in the study, then his or her enrolment code cannot be reused.

4.4 Withdrawal of patients from study

4.4.1 Permanent discontinuation of procedure

Patients may be discontinued from study in the following situations:

- Patient decision.
- Investigator decision.
- Patient did not undergo ^{89}Zr -TLX250 PET/CT imaging study procedure.

4.4.2 Withdrawal of consent

Patients are free to withdraw from the study at any time (study procedure and assessments) without prejudice to their further medical care.

In case of withdrawal of consent, the patient's study generated data may be used until withdrawal of consent date, unless the patient has objected.

